### 8.3. At any course:

**In case of suspected thrombus:** D-Dimers testing will be performed.

**In case of suspected haemolysis based on biological tests** [Hb, haptoglobin, LDH, total and free bilirubin levels (total bilirubin in all patients; if total bilirubin >ULN, free bilirubin will be assessed from the same blood sample, as total bilirubin)]: Reticulocytes and direct Coombs test will be performed.

### 8.4. Central Biological Handling Sampling

Details for blood sampling performed for the biomarkers (anti-CNTN1, anti-NF155 antibodies, BAFF, CH50), storage and shipment to the central laboratory are described in the laboratory manual.

### 8.5. Ultrasonography (for Italian site only)

Details for ultrasonography coupled to neurophysiology examination are described in the ultrasonography manual.

## **8.6. Compliance with the Study Plan**

The Investigator should make every effort to comply with the study plan. If the Investigator encounters difficulties in complying with the study plan, e.g. with regard to the schedule of visits or the required procedures, he/she must alert the Sponsor. The Sponsor may consider it relevant to generate an amendment.

The Investigator should make every effort to avoid the occurrence of deviations from the study plan. If deviations occur or if the Investigator knows that a deviation will occur, he/she must promptly inform the Sponsor to determine how to manage the deviation.

## **9. SAFETY**

### **9.1. Reference Safety Information Document**

The current version of the Investigator Brochure of I10E, will be the Reference Safety Information document to assess the expectedness of AEs.

### **9.2. Benefit / Risk Information**

#### **9.2.1. Potential Risk(s) Related to the Study Drug**

Common and important adverse reactions associated with IVIg administration are described in the European Guideline EMA/CHMP/BPWP/94038/2007 rev.4 of IVIg [18].

Adverse reactions such as chills, headache, dizziness, fever, vomiting, allergic reactions, nausea, arthralgia, low blood pressure and moderate low back pain may occur occasionally with IVIg.

Rarely human normal Ig may cause a sudden fall in blood pressure and, in isolated cases, anaphylactic reaction, even when the patient has shown no hypersensitivity to previous administration.

Cases of reversible aseptic meningitis and rare cases of transient cutaneous reactions have been observed with human normal immunoglobulin. Reversible haemolytic reactions have been observed in patients, especially those with blood groups A, B, and AB. Rarely, haemolytic anaemia requiring transfusion may develop after high dose IVIg treatment.

Increase in serum creatinine level and/or acute renal failure have been observed.

Very rarely, thromboembolic reactions such as myocardial infarction, stroke, pulmonary embolism, deep vein thromboses have been described.

Important potential risks that could be anticipated with I10E administration are those known with IVIg preparations:

#### **Hypersensitivity**

True hypersensitivity reactions are rare. They can occur in patients with anti-IgA antibodies.

Rarely, human normal immunoglobulins can induce a fall in blood pressure with anaphylactic reaction, even in patients who had tolerated previous treatment with human normal immunoglobulins.

To minimize risk of anaphylactic reactions, patients with IgA deficiency will be excluded, except if the absence of anti-IgA antibodies is documented. The patients with a known hypersensitivity to the active substance or to any of the excipients of I10E will be excluded.

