EXCLUSION CRITERIA	
Based on follow-up and results of analyses performed in PRISM I10E-1302 study, a patient may be eligible in PRISM 2 I10E-1306 study if none of the following criteria is met:
 
 
1. History of severe allergic reaction or serious adverse reaction to any Ig.
 
2. Known hypersensitivity to human Ig or to any of the excipients of I10E (glycine and polysorbate 80).
 
3. History of cardiac insufficiency (New York Heart Association (NYHA) III/IV), uncontrolled cardiac arrhythmia, unstable ischemic heart disease, or uncontrolled hypertension.
 
4. History of venous thromboembolic disease, myocardial infarction or cerebrovascular accident.
 
5. Risk factor for blood hyperviscosity such as cryoglobulinemia or haematological malignancy with monoclonal gammopathy.
 
6. History of personal or familial congenital thrombophilia or acquired thrombophilia.
 
7. Factors contributing to venous stasis such as long-term bed confinement.
 
8. Body Mass Index (BMI) <math>\geq 40</math> kg/m^2.
 
9. Protein-losing enteropathy characterised by total serum protein level <math>< 60</math> g/L and serum albumin levels <math>< 30</math> g/L.
 
10. History of kidney transplantation, nephrotic syndrome (defined as proteinuria <math>> 3.5</math> g per 24 hours accompanied by hypoalbuminemia and edema), or any acute or chronic kidney disease that in the opinion of the investigator and/or nephrologist would preclude the use of I10E and/or interfere with the assessment of the safety and efficacy of I10E.
 
 
AND/OR
 
Chronic kidney disease (CKD) for more than 3 months as documented by at least one of the following:
 
 
* glomerular filtration rate (GFR) <math>< 60</math> mL/min/1.73m^2 measured according to the Modified Diet in Renal Disease (MDRD) formula
 
 
AND/OR
 
 
* urine protein reagent strip: <math>\geq 2</math> crosses
 
 
AND/OR
 
 
* urine protein reagent strip: one cross with one of the following: 
 
▪ albumin excretion rate (AER) <math>> 300</math> mg/24 hours or protein excretion rate (PER) <math>> 500</math> mg/24 hours (24h-urine collection)
 
 
 

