### **5.2. Eligibility Criteria**

Before any study-related procedure is undertaken, written informed consent must be obtained (see Section [8.1.1](#))

A patient is eligible if all the inclusion criteria and none of the exclusion criteria are met.

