### 5.2.2. Exclusion Criteria

Based on follow-up and results of analyses performed in PRISM I10E-1302 study:

1. History of severe allergic reaction or serious adverse reaction to any Ig.
2. Known hypersensitivity to human Ig or to any of the excipients of I10E (glycine and polysorbate 80).
3. History of cardiac insufficiency (NYHA III/IV), uncontrolled cardiac arrhythmia, unstable ischemic heart disease, or uncontrolled hypertension.
4. History of venous thromboembolic disease, myocardial infarction or cerebrovascular accident.
5. Risk factor for blood hyperviscosity such as cryoglobulinemia or haematological malignancy with monoclonal gammopathy.
6. History of personal or familial congenital thrombophilia or acquired thrombophilia.
7. Factors contributing to venous stasis such as long-term bed confinement.
8. Body Mass Index (BMI)  $\geq 40$  kg/m^2.
9. Protein-losing enteropathy characterised by total serum protein level  $< 60$  g/L and serum albumin levels  $< 30$  g/L.
10. History of kidney transplantation, nephrotic syndrome (defined as proteinuria  $> 3.5$  g per 24 hours accompanied by hypoalbuminemia and edema), or any acute or chronic kidney disease that in the opinion of the investigator and/or nephrologist would preclude the use of I10E and/or interfere with the assessment of the safety and efficacy of I10E.

AND/OR

Chronic kidney disease (CKD) for more than 3 months as documented by at least one of the following:

- glomerular filtration rate (GFR) <60 mL/min/1.73m^2 measured according to the Modified Diet in Renal Disease (MDRD) formula

AND/OR

- urine protein reagent strip: ≥2 crosses

AND/OR

- urine protein reagent strip: one cross with one of the following:
  - albumin excretion rate (AER) >300 mg/24 hours or protein excretion rate (PER) >500 mg/24 hours (24h-urine collection)

OR

- albumin to creatinine ratio (ACR) >30 mg/mmol or protein to creatinine ratio (PCR) >50 mg/mmol (spot urine sample).

11. Serum levels of alanine aminotransferase (ALT) or aspartate aminotransferase (AST) >2 times upper limit of normal (ULN) range.

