12. Any other ongoing disease that may cause chronic peripheral neuropathy, such as toxin exposure, dietary deficiency, uncontrolled diabetes, hyperthyroidism, cancer, systemic lupus erythematosus or other connective tissue diseases, infection with HIV, Hepatitis B Virus (HBV) or Hepatitis C Virus (HCV), Lyme disease, multiple myeloma, Waldenström's macroglobulinaemia, amyloidosis, and hereditary neuropathy.

13. Woman with positive results on a urine pregnancy test or breastfeeding woman or woman of childbearing potential without an effective contraception.

Effective contraceptives are injectable, patch or oral combined oestro-progestative or progestative contraceptives, Copper T or levonorgest releasing intra-uterine devices, depot intramuscular medroxyprogesterone, subcutaneous progestative contraceptive implants, condoms or occlusive caps (diaphragm or cervical/vault caps) with spermicide, true abstinence (when this is in line with the preferred and usual lifestyle of the patient).

14. Any other serious medical condition that would interfere with the clinical assessment of CIDP or use of I10E or prevent the patient from complying with the protocol requirements.

15. Increasing dosage or introduction of a systemic corticosteroids therapy, or corticosteroids therapy at a dose higher than 10 mg prednisolone per day, or equivalent within the last 3 months prior to screening (in I10E-1302 Clinical Study). Topical corticosteroids are permitted.

16. Treatment within 12 months prior to screening with immunomodulatory or immunosuppressant agents (including but not limited to cyclophosphamide, cyclosporine, interferon- $\alpha$ , interferon- $\beta$ 1a, anti-CD20, alemtuzumab, aziathioprine, etanercept, mycophenolate mofetil and methotrexate) or haemopoetic stem cell transplantation.

17. Plasma exchange, blood products or derivatives administered within the last 3 months prior to screening.

18. Drug or alcohol abuse.

19. Anticipated poor compliance of patient with study procedures.

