#### Thromboembolism

There is clinical evidence of an association between IVIg administration and thromboembolic events such as myocardial infarction, cerebral vascular accident (including stroke), pulmonary embolism and deep vein thromboses. Such an association is assumed to be related to a relative increase in blood viscosity through the high influx of immunoglobulins in at-risk patients.

To minimize the risk of thrombo-embolic events, patients with a history of venous thrombo-embolic disease, myocardial infarction or cerebrovascular accident will be excluded. As well, patients with uncontrolled cardiac arrhythmia and patients with unstable ischemic heart disease will not be allowed to participate to the study.

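### The safety section excludes IgA-deficient patients without documented absence of anti-IgA antibodies, but the eligibility lists in Protocol 5.2.2 and the synopsis omit this exclusion

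*Protocol*

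**What the plan says.** Protocol 9.2.1, under Hypersensitivity, notes that true hypersensitivity reactions can occur in patients with anti-IgA antibodies. To reduce the risk of anaphylaxis it then commits that "patients with IgA deficiency will be excluded, except if the absence of anti-IgA antibodies is documented". A separate sentence in the same place excludes patients with known hypersensitivity to the active substance or the excipients.

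Eligibility is decided elsewhere. Section 5.2 sets the test: "A patient is eligible if all the inclusion criteria and none of the exclusion criteria are met". The synopsis words it similarly: "a patient may be eligible in PRISM 2 I10E-1306 study if none of the following criteria is met". Section 5.2.2 introduces its list with "Based on follow-up and results of analyses performed in PRISM I10E-1302 study", so the criteria are judged from what the parent study has already recorded.

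Neither list refers to IgA deficiency or to anti-IgA antibodies. The visit procedures in 8.2 and the study plan table schedule total IgG trough levels, but no IgA or anti-IgA test.

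**The concern.** The protocol gives two answers to one question. Under 9.2.1, an IgA-deficient patient whose anti-IgA antibodies have not been shown to be absent must not enter. Under 5.2, the same patient is eligible if the listed criteria are satisfied. An investigator working through the eligibility list would not be prompted to check IgA status, and no study visit would supply the result.

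Reporting is affected too. SAP 3.5.2 classifies deviations by category, one of which is deviations from exclusion criteria. Entry of an IgA-deficient patient would breach no listed criterion, so it could go unrecorded unless it was reported as another kind of deviation.

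What is at stake is a safety safeguard and the report's account of it. The responder rate and its confidence interval are not involved.

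**Working it through.** There is no figure to reproduce; the check is a comparison of texts.

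**Step 1. Trace each patient exclusion in 9.2.1 to the eligibility list.**

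| Exclusion stated in 9.2.1 | Place in 5.2.2 |
|---|---|
| IgA deficiency without documented absence of anti-IgA antibodies | none |
| Known hypersensitivity to the active substance or excipients | criterion 2 |
| Venous thromboembolism, myocardial infarction or cerebrovascular accident | criterion 4 |
| Uncontrolled arrhythmia or unstable ischaemic heart disease | criterion 3 |
| Chronic kidney disease | criterion 10 |

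Stated: 5. Carried over: 4. Missing: 5 − 4 = 1.

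The thromboembolism row shows how the transfer normally works. Section 9.2.1 says "patients with a history of venous thrombo-embolic disease, myocardial infarction or cerebrovascular accident will be excluded", and criterion 4 reads "History of venous thromboembolic disease, myocardial infarction or cerebrovascular accident". The IgA sentence has no such partner. Section 9.2.1 also restricts loop diuretics. That rule is not in 5.2.2 either, but it is made operative in 7.1 and 7.2 by postponing the infusion.

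**Step 2. Search the lists for the rule in any form.**

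- 5.2.1: 0 of 4 inclusion criteria mention IgA deficiency or anti-IgA antibodies.
- 5.2.2: 0 of 19 exclusion criteria.
- Synopsis: 0 of 4 and 0 of 19.

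**Step 3. See whether another criterion contains it.** Criterion 1 needs a past severe or serious reaction to an immunoglobulin. Criterion 2 needs known hypersensitivity, which 9.2.1 treats in a separate sentence from IgA deficiency. Criterion 14 bars "Any other serious medical condition that would interfere with the clinical assessment of CIDP or use of I10E". It could be applied to such a patient, but it states neither the IgA rule nor the anti-IgA exception.

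**Step 4. See whether another section supplies it.** Section 7.1 adds entry restrictions, but on medication only.

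**Step 5. Gauge the exposure.** Every entrant is a responder who completed the last visit of I10E-1302 (5.2.1). The regimen there was one dose of 2 g/kg and then seven of 1 g/kg (1.3.2 and 1.4), a planned total of 2 + 7 × 1 = 9 g/kg. Each dose in the extension is 0.5 g/kg: half the parent maintenance dose and a quarter of its first dose. The expected number of entrants is 15 to 30 (5.1). How many, if any, were IgA-deficient is not stated.

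**The case against.** The strongest reply is that the rule is in the protocol, in mandatory wording, and that section 16.1 binds investigators to the whole protocol. Section 7.1 shows that entry restrictions can sit outside 5.2.2; it bars recent use of other investigational products, which 5.2.2 does not list. This has some force, but 5.2 still defines eligibility by the listed criteria, and a general duty to follow the protocol does not settle which of two conflicting rules governs.

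A second reply is that I10E-1302 probably dealt with the matter. All entrants come from it, and the extension's criteria are judged on its results. SAP 4.7.3 names serum IgA as a laboratory parameter although no extension visit collects it, while SAP section 3 combines the two studies' databases. That hints at measurement in the parent study. It does not prove measurement, still less that the exclusion was applied, and the parent study's criteria are not in these documents. If the rule was applied there, what remains is a missing cross-reference.

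Two stronger readings are tempting and should be resisted:

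- A reader might dismiss criterion 14 as optional. It carries no opinion-of-the-investigator qualifier, unlike part of criterion 10. Applying it takes judgement, but the exclusion is not worded as discretionary. Its weakness here is only that it does not state the IgA rule.
- A reader might take the 9.2.1 warning that anaphylactic reactions can occur "even in patients who had tolerated previous treatment with human normal immunoglobulins" as evidence that IgA-deficient entrants remain at material risk. That sentence concerns immunoglobulins generally. It does not show how much risk an IgA criterion would remove among patients who have already tolerated I10E.

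It also stands that criteria 1 and 2, together with the slow starting rate, monitoring and emergency handling in 9.3 and 9.4, give protection that does not depend on the missing criterion.

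**Conclusion.** The conflict is real. Section 9.2.1 promises an exclusion that the eligibility lists do not contain, so the safeguard is not operative at entry through the criteria that decide entry. It is one of five patient exclusions in 9.2.1, and the only one not carried over.

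Its practical weight is small. The number of patients affected is unknown and may be zero; it is zero if I10E-1302 applied the rule. Residual risk is low because entrants completed the parent study on a regimen with higher doses. Efficacy results are unaffected.

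A reader might infer that unprotected IgA-deficient patients were in fact enrolled. The documents do not support that: they show an omission from the lists and give no information on any entrant's IgA status. Confidence is high on the omission, and no conclusion can be drawn on harm. The serum IgA entry in SAP 4.7.3 is a separate housekeeping matter and forms no part of this point.

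**What to change.** Add to 5.2.2 and the synopsis an exclusion for IgA deficiency, with the exception for documented absence of anti-IgA antibodies, to be judged from existing I10E-1302 records. If I10E-1302 already applied the rule at entry, a sentence in 9.2.1 saying so resolves the conflict instead.

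SAP 4.10 records that the study was terminated early, so the step with remaining value is in the study report: state the IgA status of the entrants, or state that it was not documented.

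During recruitment, the change to 5.2.2 would have meant a protocol amendment across the seven participating countries, with no new test if existing records were used. Now the cost is a check of records for the entrants (15 to 30 expected) and one statement in the report.

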#### Thromboembolism

There is clinical evidence of an association between IVIg administration and thromboembolic events such as myocardial infarction, cerebral vascular accident (including stroke), pulmonary embolism and deep vein thromboses. Such an association is assumed to be related to a relative increase in blood viscosity through the high influx of immunoglobulins in at-risk patients.

To minimize the risk of thrombo-embolic events, patients with a history of venous thrombo-embolic disease, myocardial infarction or cerebrovascular accident will be excluded. As well, patients with uncontrolled cardiac arrhythmia and patients with unstable ischemic heart disease will not be allowed to participate to the study.

#### Acute renal failure

Cases of acute renal failure have been reported in patients receiving IVIg therapy. In most cases, risk factors have been identified. These included pre-existing renal insufficiency, diabetes mellitus, hypovolaemia, overweight, concomitant nephrotoxic medicinal products and age over 65.

To minimize the risk of acute renal failure, patients with a chronic kidney disease (CKD) defined as abnormalities of kidney structure or function, present for >3 months, with implications for health, i.e. patients with persistent albuminuria category A3 and/or GFR <60 mL/min/1.73m^2 (measured according to the MDRD calculation) [31] will be excluded.

The use of loop diuretics is also not allowed if used within 24 hours prior to study drug administration.

#### Aseptic meningitis syndrome (AMS)

Aseptic meningitis syndrome has been reported to occur in association with IVIg treatment.

Discontinuation of IVIg treatment has resulted in remission of AMS within several days without sequelae. AMS may occur more frequently in association with high-dose of IVIGs.

#### Haemolytic anaemia

IVIg products can contain blood group antibodies which may act as haemolysins and induce in vivo coating of red blood cells with immunoglobulin, causing a positive direct antiglobulin reaction (Coombs' test) and, rarely, haemolysis. Haemolytic anaemia can develop subsequent to IVIg therapy due to enhanced red blood cells (RBC) sequestration.

Haptoglobin and LDH levels in patients will be assessed at every visit.

#### Interference with serological testing

After injection of immunoglobulin the transitory rise of various passively transferred antibodies in the patient's blood may result in misleading positive results in serological testing.

Passive transmission of antibodies to erythrocyte antigens, e.g. A, B, D may interfere with some serological tests for red cell antibodies for example the direct antiglobulin test (DAT), direct Coombs' test.

### Interaction with other medicinal products

I10E may impair the efficacy of live attenuated virus vaccines for a period of up to 3 months. In the case of measles, this impairment may persist for up to 1 year.

### Transmissible agents

Despite dedicated effective measures to prevent infections resulting from the use of plasma-derived products including selection of donors, screening of individual donations and plasma pools, as well as effective manufacturing steps for the inactivation/removal of viruses, the risk of transmitting infective agents cannot be totally excluded. This also applies to unknown or emerging viruses and other pathogens.

Patient serum reference samples will be drawn at the beginning and at the end of the study, and will be kept for long term storage.

### **9.2.2. Potential Risks Related to the Study Procedures**

Blood sampling will be performed during this study in order to monitor the safety. Although this procedure represents an inconvenience for the patient, it does not constitute an additional significant risk.

There is a minor risk of haematoma from intravenous infusion of the study drug and from drawing blood. Slight pain at the injection site, feeling light-headed, bruising and, exceptionally, infection as well as bleeding from the site of the puncture may occur.

### **9.3. Risk Minimisation Actions Throughout the Protocol**

Some adverse drug reactions may be related to the infusion flow rate. Patients will be closely monitored and carefully observed for any symptoms throughout the infusion periods. In the case of AE, the infusion rate may be reduced or even stopped. Standard medical care should be implemented as necessary.

Potential complications will be avoided by ensuring that patients:

- have an adequate hydration status prior to infusions of the study drug;
- are not sensitive to human normal Ig by initially infusing the product slowly, starting at 0.5 mL/kg/h during the first 30 minutes;
- are carefully monitored for any symptoms throughout the infusion period and 30-45 minutes after the end of each infusion. An additional phone call at 4 days (+/- 1 day) from the Investigator or the Study Nurse to the patient is planned to ask if AEs or TAAEs are reported within 72 hours after the end of each course;
- Close Monitoring (vital signs, biological tests, haematological tests, physical examinations planned for each course to minimise these risks);
- D-Dimers, in case of suspected thrombus;
- Reticulocytes and Direct Coombs test, in case of haemolysis based on biological tests [Hb, haptoglobin, LDH, total and free bilirubin levels (total bilirubin in all patients; if total bilirubin > ULN, free bilirubin will be assessed from the same blood sample, as total bilirubin)].

